3.4 Exploratory Objectives

These objectives may be explored to characterize participants receiving MDMA-assisted psychotherapy to support the primary objective:

- 1. Explore the effect of presence of secondary traumatic stressors (LEC-5) on the CAPS-5 Total Severity analyses
- Explore changes within-participants in PTSD symptom clusters of re-experiencing, avoidance, negative alterations in cognition and mood, and hyperarousal, as measured by changes in CAPS-5 subscale scores from Visit 3 (Baseline) to Visit 14 (13 weeks post Baseline)
- 3. Explore the effect of adverse childhood experiences (ACE) on the CAPS-5 Total Severity analyses
- 4. Explore changes in:
 - Dissociative symptoms associated with PTSD (DSP-I)
 - Depression (BDI-II)
 - Chronic pain (CPGS)
 - Quality of life (EQ-5D-5L)
 - Self-compassion (SCS)
 - Addictive behaviors including: alcohol use (AUDIT), drug use (DUDIT), and nicotine use (SRNU)
 - Eating habits (EAT-26)

- Healthcare utilization (UFEC) and economic productivity
- Subjective effects (SE)

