Assess changes in quality of life from Visit 4 to Visit 15	EQ-5D-5L	Outcome	Site		
Assess changes in self-compassion from Visit 4 to Visit 15	SCS	Outcome	Site		
Assess changes in subjective effects from prior to drug intake, peak and at the end of the experimental session	SE	Subjective effects	Self-report measure at Site		
Assess changes in alcohol use from Screening to Visit 15	AUDIT	Healthcare cost	Site		
Assess changes in drug use from Screening to Visit 15	DUDIT	Healthcare cost	Site		
Assess changes in nicotine use from Visit 4 to Visit 15	SRNU	Healthcare cost	Site		
Assess changes in disordered eating from Visit 4 to Visit 15	EAT-26	Healthcare cost	Site		
Assess facility-based healthcare utilization and economic productivity at Screening	UFEC	Healthcare cost	Site		

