#### Utilization of Facility-based and Emergent Care (UFEC) and Economic Productivity

The UFEC is a sponsor-developed measure assessing participant health events, including hospitalization and use of healthcare facilities, including in-patient hospitalization, rehabilitation facilities and other health care facilities for a set period prior to study entry.

In addition, participants employment/disability status and income level will be collected in order to assess economic productivity.

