5.0 Study Design

Table 1: Dose Regimen of MDMA

Experimental Session	Initial Dose	Supplemental Dose*	Min-Max Cumulative Dose
1	80 milligrams (mg)	40 mg	80 mg to 120 mg
2	80 or 120* mg	40 or 60 mg	80 mg to 180 mg
		Total Cumulative Dose	160 mg to 300 mg

* Unless contraindicated

Table 2: Time and Events – Study Procedures

			ing Period 6 weeks)		Preparatory Period w/ Enrollment Confirmation (2 to 11 weeks)						
		Screening	,	Enrollment V0	-	ratory	Baseline CAPS-5 T1	Baseline & Enrollment Confirmation			
Visit	Phone Screening	Screening	IR Screening		V1	V2	V3	V4			
Visit Description	Phone Calls	In-person Visits & Labs	Tele- assessment	Enrollment	Prep. 1	Prep. 2	Tele- assessment	Prep. 3 & Enrollment Confirmation			
Visit Timing	Prior to Initial Screening	Over 3 weeks (-2 /+1 weeks)	2 days after initial eligibility met (+7 days)	2 days post IR Screening (+12 days)	Within 1 week of V0 (0 to 12 days)	2 to 21 days of V1	Post V2 & Taper	3 to 6 days after V3; 1 to 4 days before V5			
Initial Phone Screen	\checkmark										
Informed Consent	Send Copy	\checkmark									
Follow-up Phone Screen	\checkmark										
Assess Eligibility	\checkmark	\checkmark		\checkmark	\checkmark	\checkmark		\checkmark			
Medical/Psychiatric History	✓ A	\checkmark			\checkmark	\checkmark		\checkmark			
Past/Current Medication & Adherence	\checkmark	\checkmark			\checkmark	\checkmark		\checkmark			
Weight, Resting Vitals		\checkmark									
Physical Exam		\checkmark									
ECG & Rhythm Strip		\checkmark									
Clinical Lab Tests		\checkmark									
Drug Screen		\checkmark						\checkmark			
Pregnancy Screen		\checkmark						\checkmark			
Enter Participant in eCRF ^B		\checkmark									
Record			\checkmark		\checkmark	\checkmark	\checkmark	\checkmark			
Medication Taper				\checkmark	\checkmark	\checkmark					
Study Enrollment				\checkmark				✓ Confirmed			
All AEs ^C				\checkmark	\checkmark	\checkmark		\checkmark			
90-min Preparatory Session					\checkmark	\checkmark		\checkmark			
Phone Call Follow-up D						\checkmark					

^A At Screening, collect data on previous hospitalizations, healthcare utilization and economic productivity. Request participants to obtain medical/psychiatric records to bring to the in-person screening. ^B Participants will be entered into the eCRF after the IR visit is scheduled

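### Change in healthcare utilization and economic productivity is an optional exploratory objective, but both are scheduled only before the first dose

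*SAP*

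**What the plan says.** SAP 3.4, item 4, opens with "Explore changes in" and includes "Healthcare utilization (UFEC) and economic productivity" in the list that follows. Protocol 2.4 and the protocol synopsis carry the same item. In all three places the lead-in makes the objectives optional.

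The operational sections treat the item differently:

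- Protocol Table 4 gives its purpose as "Assess facility-based healthcare utilization and economic productivity at Screening". A neighbouring row reads "Assess changes in nicotine use from Visit 4 to Visit 15".
- Protocol 6.5 describes UFEC as covering facility use "for a set period prior to study entry", and adds that "participants employment/disability status and income level will be collected in order to assess economic productivity", without naming a visit.
- SAP Table 2 (section 5.0), footnote A, reads "At Screening, collect data on previous hospitalizations, healthcare utilization and economic productivity". Protocol Table 5 (footnote B) and protocol 7.1.1 give the same instruction.
- Protocol 7.2.3 puts UFEC and economic productivity on the Visit 4 baseline list. Visit 4 is also the only UFEC tick in protocol Table 7 and SAP Table 3.
- The Visit 15 self-report list in protocol 7.4.3 contains neither.

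**The concern.** A change needs one value before treatment and one after it. If both measures are taken only before dosing, the plan can be followed exactly and still produce nothing for this item. Both documents would then state an objective that the schedule cannot serve, and the gap would be found only at analysis, when the data could no longer be collected. What is at stake is this one exploratory item, not the primary or secondary analysis.

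**Working it through.** **Step 1. Is the missing Visit 15 tick real?** The tables were read from PDF, so a tick could have moved. The stated time totals give a check, using the minutes per measure in protocol Table 7 and SAP Table 3.

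Visit 15, items ticked: C-SSRS 10 + LEC-5 5 + PCL-5 8 + BDI-II 5 + CPGS 5 + EQ-5D-5L 3 + SCS 6 + AUDIT 3 + DUDIT 3 + SRNU 3 + EAT-26 6 = **57**. The stated total is 57. With UFEC (3 minutes) it would be 57 + 3 = 60.

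Screening, items ticked: C-SSRS 10 + CIPD-SR 20 + LEC-5 5 + PCL-5 8 + AUDIT 3 + DUDIT 3 = **49**. The stated total is 49. With UFEC it would be 52.

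The totals therefore exclude UFEC from both Visit 15 and the Screening site visit, and the prose list in protocol 7.4.3 independently confirms the Visit 15 omission. The Visit 4 total cannot be used in this way: its ticked items sum to 10 + 5 + 8 + 4 + 10 + 5 + 3 + 6 + 3 + 6 + 3 = 63, against a stated 50. The Visit 4 collection rests instead on the tick in both tables and the list in 7.2.3.

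**Step 2. When is each item on the list of changes measured?**

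| Item | Before first dose | After dosing starts |
|---|---|---|
| DSP-I | Visit 3 | Visits 8, 14 |
| BDI-II, CPGS, EQ-5D-5L, SCS, SRNU, EAT-26 | Visit 4 | Visit 15 |
| AUDIT, DUDIT | Screening | Visit 15 |
| SE | Pre-dose in each session | During and at end of each session |
| UFEC and economic productivity | Screening and/or Visit 4 | None |

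UFEC and productivity form the only item with an empty right-hand column.

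**Step 3. Could the two pre-treatment collections give a change?** Visit 4 falls 1 to 4 days before Experimental Session 1 (protocol Table 1). A difference between Screening and Visit 4 would describe the run-in and medication taper, not treatment.

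**Step 4. Could the form reach back over the treatment period?** Not as described: its reference period ends at study entry.

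**Result.** Scheduled post-treatment assessments of UFEC or productivity: 0. Participants with a computable change across treatment: 0 of up to 40.

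**The case against.** The best defence is that this is one bullet under the wrong heading. Table 4, the UFEC description in 6.5 and the Visit 15 list all point to a pre-treatment characteristic, and the lead-in to the objectives speaks of characterizing participants. The objective is optional, and the text of SAP 8.7.3 specifies no UFEC or productivity analysis beyond the general descriptive statistics of SAP 8.7. This stands, and it limits the consequence. It supports rewording as a sufficient remedy, but it does not remove the conflict between the objective and the schedule.

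A reader might infer that healthcare use during the study goes unobserved. The documents do not support that. SAEs, including hospitalizations, are collected from consent to Study Termination (protocol 10.1.2). SAP 8.8.2 has a category for events leading to hospitalization. AE assessment covers events needing medical attention, and participants agree to report medical treatments within 48 hours. However, neither document plans to use these data for this objective, and they contain no measure of employment or income. The long-term follow-up extension mentioned in protocol 7.4.3 is a separate study.

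A reader might also assume that the pre-entry and on-study recall periods differ in length. Protocol 6.5 gives no length, so this is unknown.

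Finally, one may ask what a change over roughly 13 weeks in hospital use or income would show in a small uncontrolled sample. The documents do not say. That is a fair reason to prefer rewording over new data collection.

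**Conclusion.** The point holds as an inconsistency between a stated objective and the schedule, present in both documents. No participant will have a scheduled post-treatment value for UFEC or economic productivity, so no change across treatment can be computed. The conclusion rests on the scheduled visits named in the documents. The one gap is that protocol 6.5 gives no visit for the employment and income items, but Screening and Visit 4 are the only visits named elsewhere for economic productivity.

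The importance is low. The item is exploratory and optional, and it would be wrong to infer that any effectiveness or safety conclusion is affected.

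There is a secondary inconsistency in the pre-treatment timepoint: Table 4 says Screening, while protocol Table 7 and SAP Table 3 say Visit 4.

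**What to change.** Choose one of two.

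1. **Collect it.** Add UFEC and the employment or disability status and income items at Visit 15, with a defined on-study reference period, and state the length of the pre-entry period as well. Report utilization as counts per unit time if the reference periods differ. They would differ between participants if, for example, the on-study period ran from Visit 3 to Visit 15, because that window is 68 to 121 days (121/68 = 1.8-fold). Report employment and income as change in status or level, since rates do not suit them. Cost: about 3 minutes for UFEC, taking Visit 15 measures from 57 to 60 minutes (3/57 = 5.3%), plus the employment and income items, for which no time is given. UFEC as described covers only the period before entry, so the form and the eCRF also need updating.

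2. **Reword it.** Remove the item from the list of changes in the synopsis, protocol 2.4 and SAP 3.4, and report it as a baseline characteristic under SAP 8.6. Cost: a wording change and no new data. If participants have already passed Visit 15, this is the practical choice.

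Under either option, make Table 4 agree with protocol Table 7 and SAP Table 3 on whether the pre-treatment value comes from Screening or Visit 4.

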4.0 Measures

4.1 Primary Measure

• Clinician Administered PTSD Scale for DSM-5 (CAPS-5)

4.2 Secondary Outcome Measure

• Sheehan Disability Scale (SDS)

4.3 Safety Measures

- Treatment-emergent Adverse events
- Concomitant medication use
- Vitals signs during MDMA sessions
- Columbia Suicide Severity Rating Scale (C-SSRS)

4.4 Exploratory Measures

- Life Events Checklist (LEC-5)
- Adverse Childhood Experience Questionnaire (ACE)
- Dissociative symptoms associated with PTSD (DSP-I)
- Depression (BDI-II)
- Chronic pain (CPGS)
- Quality of life (EQ-5D-5L)
- Self-compassion (SCS)
- Addictive behaviors including: alcohol use (AUDIT), drug use (DUDIT), and nicotine use (SRNU)
- Eating habits (EAT-26)
- Healthcare utilization (UFEC)
- Subjective effects (SE)

5.0 Study Design

Table 1: Dose Regimen of MDMA

Experimental Session	Initial Dose	Supplemental Dose*	Min-Max Cumulative Dose
1	80 milligrams (mg)	40 mg	80 mg to 120 mg
2	80 or 120* mg	40 or 60 mg	80 mg to 180 mg
		Total Cumulative Dose	160 mg to 300 mg

* Unless contraindicated

Table 2: Time and Events – Study Procedures

			ing Period 6 weeks)		Preparatory Period w/ Enrollment Confirmation (2 to 11 weeks)						
		Screening	,	Enrollment V0	-	ratory	Baseline CAPS-5 T1	Baseline & Enrollment Confirmation			
Visit	Phone Screening	Screening	IR Screening		V1	V2	V3	V4			
Visit Description	Phone Calls	In-person Visits & Labs	Tele- assessment	Enrollment	Prep. 1	Prep. 2	Tele- assessment	Prep. 3 & Enrollment Confirmation			
Visit Timing	Prior to Initial Screening	Over 3 weeks (-2 /+1 weeks)	2 days after initial eligibility met (+7 days)	2 days post IR Screening (+12 days)	Within 1 week of V0 (0 to 12 days)	2 to 21 days of V1	Post V2 & Taper	3 to 6 days after V3; 1 to 4 days before V5			
Initial Phone Screen	\checkmark										
Informed Consent	Send Copy	\checkmark									
Follow-up Phone Screen	\checkmark										
Assess Eligibility	\checkmark	\checkmark		\checkmark	\checkmark	\checkmark		\checkmark			
Medical/Psychiatric History	✓ A	\checkmark			\checkmark	\checkmark		\checkmark			
Past/Current Medication & Adherence	\checkmark	\checkmark			\checkmark	\checkmark		\checkmark			
Weight, Resting Vitals		\checkmark									
Physical Exam		\checkmark									
ECG & Rhythm Strip		\checkmark									
Clinical Lab Tests		\checkmark									
Drug Screen		\checkmark						\checkmark			
Pregnancy Screen		\checkmark						\checkmark			
Enter Participant in eCRF ^B		\checkmark									
Record			\checkmark		\checkmark	\checkmark	\checkmark	\checkmark			
Medication Taper				\checkmark	\checkmark	\checkmark					
Study Enrollment				\checkmark				✓ Confirmed			
All AEs ^C				\checkmark	\checkmark	\checkmark		\checkmark			
90-min Preparatory Session					\checkmark	\checkmark		\checkmark			
Phone Call Follow-up D						\checkmark					

^A At Screening, collect data on previous hospitalizations, healthcare utilization and economic productivity. Request participants to obtain medical/psychiatric records to bring to the in-person screening. ^B Participants will be entered into the eCRF after the IR visit is scheduled

^c All Adverse Events (AEs) includes collecting Serious Adverse Events, AEs of Special Interest, AEs of Psychiatric Status, AEs requiring medical advice or attention, AEs that indicate withdrawal of a participant, and all other AEs

^D If needed, call participant to confirm medication tapering and stabilization is complete prior to Visit 3

			Follow-up Period & Study Termination (~4 weeks) 13 weeks (+/-3 weeks) post baseline								
			Treatment	1			Treatm	ient 2	Primary Outcome	Study Termination	
Visit	V5	V6	V7	V8	V9	V10	V11	V12	V13	V14	V15
Visit Description	Exp. 1	Int. 1.1	Int. 1.2	CAPS-5 T2: Tele- assessmen t	Int. 1.3	Exp. 2	Int. 2.1	Int. 2.2	Int. 2.3	CAPS-5 T3 Outcome: Tele- assessment ¹	Study Termination
Visit Timing	Within 1 week of V3	Morning after V5	3 to 14 days after V5	18 to 30 days after V5	20 to 34 days after V5	21 to 35 days after V5	Morning after V10	3 to 14 days after V10	20 to 34 days after V10	13 weeks post V5 (+/-3 weeks)	2 days post V14 (-1/+7 days)
Past/Current Medication & Adherence	~	~	\checkmark		\checkmark	\checkmark	\checkmark	\checkmark	~		\checkmark
Drug Screen	\checkmark					\checkmark					
Pregnancy Screen	✓					\checkmark					
Record	\checkmark	\checkmark	\checkmark	✓	\checkmark	\checkmark	\checkmark	\checkmark	\checkmark	\checkmark	
All AEs ^E	~	\checkmark	\checkmark		~	\checkmark	~	\checkmark	\checkmark		\checkmark
Administer IP	~					\checkmark					
8-hour Exp. Session	~					\checkmark					
BP, Pulse, Temperature ^F	~					\checkmark					√ G
Overnight Stay	\checkmark					\checkmark					
90-min Integrative Session		~	\checkmark		\checkmark		\checkmark	~	~		
Phone Call Follow-up ^H		~					\checkmark				
Weight											\checkmark

^E All Adverse Events (AEs) includes collecting Serious Adverse Events, AEs of Special Interest, AEs of Psychiatric Status, AEs requiring medical advice or attention, AEs that indicate withdrawal of a participant, and all other AEs

^F During Experimental Sessions, vitals are measured before Investigational Product administration, immediately before the supplemental dose is administered (or would be, if supplemental dose not given), and approximately 8 hours after initial dose, and as needed

^G At Study Termination, only blood pressure needs to be measured
^H 4 days of phone call follow-up: Day 2 and 7 after the Experimental Session, with two additional calls in between

¹ All visits must be scheduled to ensure that the Primary Outcome CAPS-5 T3 assessment is within the overall window provided: 13 weeks (+/-3 weeks) post V5

Table 3: Time and Events – Study Measures

	Screening			Baseline Enrollm Confirma	ent tion	Treatment 1				Treatment 2			Follow-up & Study Termination	
	Visit #	Site ^A	IR Screening	IR V3	V4	V5	V6&7	IR V8	V9	V10	V11&12	V13	IR V14	V15
Visit Description	~Time to Complete Measure (minutes)	Site Visit	Tele- assessment	Tele- assessment	Site Visit	Exp. Session 1	Int. Sessions 1.1 & 1.2	CAPS-5 T2: Tele- assessment	Int. Session 1.3	Exp. Session 2	Int. Sessions 2.1 & 2.2	Int. Session 2.3	CAPS-5 T3: Outcome: Tele- assessment	Study Termi- nation
CAPS-5	90 (Baseline) 60 (all others)			\checkmark				\checkmark					\checkmark	
SDS	2			✓				✓					\checkmark	
DSP-I	15			√				✓	1		1		✓	
C-SSRS ^B	10	√	✓		\checkmark	√ ^C	\checkmark		\checkmark	✓ ^C	\checkmark	\checkmark		\checkmark
MINI	15		✓											
CIPD-SR	20	~												
CIPD	60		~											
LEC-5	5	√			✓				\checkmark			\checkmark		\checkmark
PCL-5	8	√			✓				✓			√		✓
DDIS D	5		✓											
ACE	4				✓									
BDI-II	10 (Baseline) 5 (all others)				~									√
CPGS	5				✓									\checkmark
EQ-5D-5L	3				~									✓
SCS	6				~									✓
AUDIT	3	✓												\checkmark
DUDIT	3	✓												\checkmark
SRNU	3				✓									\checkmark
EAT-26	6				✓									\checkmark
UFEC	3				✓									
SE	2					✓				√				
~Total Time o Measures (min		49	105	107	50	12	10	77	23	12	10	23	77	57

 ^A Ensure that LEC-5 and CIPD-SR results are sent to the Independent Rater
^B First C-SSRS is a Lifetime assessment, other assessments are Since Last Visit
^C Conducted pre- and post-IP administration, and at phone calls on Days 2 and 7 after Experimental Session
^D The relevant questions (117 to 132) from the DDIS will be asked by the Independent Rater during the IR Screening visit. The entire measure will never be administered.

6.0 Randomization and Blinding

MP18 is an open-label study with no randomization or blinding of treatment.

7.0 Sample Size and Power Considerations

MP18 is a one-arm interventional study. Thus, no power nor sample size calculations were required.

8.0 Analyses

Every effort will be made to ensure complete, accurate and timely data collection and to avoid missing data, to ensure the completeness of the data which can impact the integrity and accuracy of the final study analysis. The statistical analyses will be reported using summary tables, figures, and data listings. All analyses and tabulations will be performed using SAS® Version 9.4 or higher, and S-PLUS. In general, nominal variables will be described in terms of frequencies and percentages. Ordinal and non-normal continuous variables will be described using sample median and range.

Approximately normal variables will be described using sample mean and standard deviations and analyzed by parametric statistical tests. Except for the primary effectiveness analysis, all statistical tests will be two-sided and a difference resulting in a p-value of less than or equal to 0.05 will be considered statistically significant. All p-values will be rounded to and displayed in four decimals. If a p-value less than 0.0001 occurs it will be shown in tables as <0.0001. Data not subject to analysis according to this plan will not appear in any tables or graphs, but will be included in the data listings. Selected results may be presented graphically using standard graphical software.

8.1 Analysis Sets

- Safety: all participants who receive any IP
- All Enrolled: all participants who signed informed consent
- *Modified Intent-To-Treat (mITT):* all enrolled participants who receive IP in at least one blinded Experimental Session (Visit 5) and have at least one follow-up CAPS-5 assessment post-treatment
- *Per Protocol (PP):* all randomized participants who meet eligibility criteria, who receive IP in two Experimental Sessions, and have two follow-up CAPS-5 assessments post-treatment
- *Not Per Protocol (NPP):* all participants who are included in the mITT set but not the PP set

8.2 Missing Data Handling

All possible procedures within Good Clinical Practice (GCP) will be used to minimize Postdosing Early Termination. Based on the US Phase 2 data it is expected that up to 5% of enrolled and randomized participants will terminate early. Post-dosing Early Terminators will be compared to the Completers using baseline demographics and CAPS-5 Total Severity Score at baseline. Participants who are removed from the study after they are enrolled and receive IP but do not complete the study may fall into one of these categories: Post-Dosing Early Termination or Dropout. If the participant has received IP in at least one Experimental Session and completed one CAPS-5 assessment beyond Baseline, they will be considered evaluable. All participants who receive IP in at least one Experimental Session will be included in all safety analyses. Post-Dosing Early Termination are participants who discontinue study treatment but continue to participate in study evaluations and outcome assessments. Data collection by IRs will continue on the same schedule as planned through Study Termination visit procedures. Dropouts are defined as a participant who decides to withdraw consent. They will terminate without further follow-up. If the participant agrees, they will complete a final CAPS-5 assessment and Study Termination visit procedures. These participants are defined as dropouts who withdraw consent due to any reason after receiving at least one dose of IP and no longer participate in the study, i.e. no further contact with investigators or site staff. Data collected on study participants up to the time of withdrawal of consent will remain in the trial database in order to maintain scientific validity. All observed CAPS-5 data up to the point of discontinuation of treatment will be included in the MMRM model of the *de jure* estimand from Post-dosing Early Terminators. Participants will not be replaced. All observed CAPS-5 data from Post-dosing Early Terminators and Dropouts collected prior to and after early termination will be included in the supportive effectiveness analysis of the *de facto* estimand.

